The PUFA index had been used in prevalence study among Philipino (Monse et al. 2010), Polish (Baginska et al. 2013) and Indian (Mehta & Sumatibhalia 2014) children. The reproducibility of the index was good, with intraexaminer kappa value of 0.85 and intraexaminer kappa values ranging from 0.80 to 0.97 (Monse et al. 2010). Despite that, currently the capability of the index in meeting the intended purpose of capturing the clinical sequelae of untreated dental caries was not assessed. This limits its use in triaging patients in a large practice, or in epidemiological survey (prevalence study) of a population. Therefore, it is paramount to ensure the index performs adequately as a screening tool when compare to conventional clinical procedures in disease detection. Furthermore, the PUFA index should also be tested in an adult population since the existing literature focused only on children.

Besides PUFA, variants of indices using the same concept were developed. In an attempt to simplify PUFA, Pulpal Involvement-Roots-Sepsis (PRS) Index was modified by redefining P as caries process reached pulp chamber, R as non-restorable caries. Also, Fistula and Abscess were combined as S (Baginska & Stokowska 2013). On the other hand, the Caries Spectrum and Treatment (CAST) Index was developed to combine both ICDAS II and PUFA (Frecken et al. 2011), but this resulted in a complex index with ten codes.

Other than indices, more accurate measurements such as radiographs were sometimes used as a screening tool for pulpal and periapical diseases. In fact, radiological assessment is crucial because chronic apical periodontitis often develops without subjective symptoms (Huumonen & Ørstavik 2002). However, there is no standard criteria for the registration of apical periodontitis in surveys and epidemiological study, either for periapical radiographs or panoramic radiographs. This makes comparison between studies difficult. With the validated Periapical Index (PAI), calibrated observers could use it for such purpose (Huumonen & Ørstavik 2002). Nevertheless,

periapical and panoramic radiographs were reported with high specificity (0.98 and 1.00, respectively) but low sensitivity (0.55 and 0.28, respectively) when compared against CBCT (Estrela et al 2008). Hence, the use of these conventional imaging tends to detect only advanced lesions and therefore underestimate disease prevalence.

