To evaluate the reliability and accuracy of PUFA and PAI in screening for clinical outcomes of untreated caries, specifically pulpal and periapical diseases.

Specific Objectives:

- a. To determine the intra- and inter-examiner reliability of PUFA in screening pulpal and periapical diseases.
- b. To determine the intra- and inter-examiner reliability of PAI in screening pulpal and periapical diseases.
- c. To determine the sensitivity, specificity and predictive values of PUFA in screening pulpal and periapical diseases.
- d. To determine the sensitivity, specificity and predictive values of PAI in screening pulpal and periapical diseases.
- e. To compare the accuracy of PUFA and PAI in screening pulpal and periapical diseases.

Methods

Participants

The study will be carried out in Primary Care Clinic, Univeristi Kebangsaan Malaysia. Consecutive sampling will be used, all eligible patients are invited to participate. The inclusion criteria are as follow:

- i. New patient, not receiving active dental treatment at the time of the study
- ii. Adult patient (18 years old or above)
- iii. Has at least 12 teeth in the oral cavity
- iv. Presented with the clinical situation for which radiograph(s) were indicated (American Dental Association 2012)
- v. No radiograph was taken within the last 6 months

At the time of this study, the UKM dental clinic routinely ordered OPG for patients with multiple dental problems, particularly if they need periodontal, prosthodontic, orthodontic treatment or oral surgery. Hence, only patients who required OPG according to the screening procedure of this institution is included. Pregnant or medically compromised patients (American Society of Anesthesiologists ASA3) will be excluded.

Sample size is estimated using the method described in Buderer (1996). Based on the systematic review, the prevalence of periapical radiolucency was about 5% (Pak et al 2012). As there was no prior data, the sensitivity of PUFA was assumed conservatively at 0.50 and specificity at 0.80. Therefore, a total of 1921 and 65 teeth are required, based on the assumed sensitivity and specificity, respectively. Since each patient must have at least 12 teeth, 161 patients will be sufficient for estimation of both sensitivity and specificity. Assuming 2% of the radiographs have

overlapped images, poor contrast or poor quality, the sample size was adjusted to a total of 165 patients.

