The unit of interest for analysis is at tooth level. A tooth is considered present in the mouth when any part of it was visible. The teeth excluded for scoring are unerupted teeth, congenitally missing teeth or supernumerary teeth, teeth removed for reasons other than dental caries, and primary teeth retained in the permanent dentition.

Reference Standard

The reference standard is the clinical diagnosis. This will be carried out by an endodontic postgraduate student, using the diagnostic criteria of AAE. Comprehensive examination will be carried out for each tooth, followed by investigation using OPG, periapical radiograph, periodontal probing, heat test, cold test, electric pulp tester when indicated, to aid in arriving at the definitive diagnosis. To observe the As Low As Reasonably Achievable (ALARA) principle, additional periapical radiographs were taken only when radiographic assessment is impossible with the OPG because of overlapping, blurred images or obscured periapical region. Because OPG has lower sensitivity than periapical radiograph in detecting apical periodontitis, periapical radiograph is also taken when periapical lesion cannot be seen on OPG but a tooth is having large caries or showing signs and symptoms of pulpal and periapical diseases. At the end of this comprehensive examination, each tooth will have pulpal and apical diagnoses.

Index Test 1: PUFA

Two independent, trained dentists are employed to screen the participants using DMFT and PUFA indices, blinded to the clinical diagnosis and PAI scoring. The examination is done using only a mouth mirror. Each tooth was scored either Decayed, Missing or Filled.

If the tooth is present, PUFA scoring is done. A particular tooth can be scored as either one of Normal, Pulpal involvement, Ulceration, Fistula or Abscess. In case of doubt concerning the extent of odontogenic infection, the basic score (Pulpal involvement) is given. Lesions in the surrounding tissues that are not related to a tooth with visible pulpal involvement as a result of caries are not recorded.

Index Test 2: PAI

The OPG will be taken for all participants by qualified radiographers using Sirona Orthophos (Sirona Dental System GmbH, Bensheim, Germany). All radiographs will be evaluated by two trained dentists, blinded to the clinical diagnoses and the PUFA scoring. Each tooth is scored for the periapical status using the Periapical Index (PAI) proposed by Ørstavik et al (1986).

Ethical consideration

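### Does taking the more sensitive periapical film only in teeth with large caries or signs and symptoms bias PUFA's apical sensitivity enough to require a change?

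*Protocol*

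**What the plan says.** The protocol's Reference Standard section says "The reference standard is the clinical diagnosis", made after a full examination of each tooth with OPG, probing and pulp tests as indicated. Periapical films are restricted on ALARA grounds to two situations. The first is an OPG that cannot be read. The second is a negative OPG in a suspicious tooth: "periapical radiograph is also taken when periapical lesion cannot be seen on OPG but a tooth is having large caries or showing signs and symptoms". The reason given is: "Because OPG has lower sensitivity than periapical radiograph in detecting apical periodontitis".

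Under Index Test 1, PUFA is scored with a mouth mirror and depends on visible caries damage: "Lesions in the surrounding tissues that are not related to a tooth with visible pulpal involvement as a result of caries are not recorded". Under Index Test 2, "All radiographs will be evaluated by two trained dentists, blinded to the clinical diagnoses and the PUFA scoring".

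The Introduction cites, against cone beam CT, sensitivity 0.55 and specificity 0.98 for periapical films, and 0.28 and 1.00 for panoramic films. Under Participants, PUFA sensitivity is assumed to be 0.50, specificity 0.80 and prevalence 5%. Data analysis plans sensitivity, specificity and predictive values per tooth. Table 4 of Appendix 2 reports them separately for the pulpal and the periapical diagnosis. No adjustment for the film rule is described.

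**The concern.** This is the pattern of differential verification. A PUFA-positive tooth has visible pulpal involvement from caries, so after a negative OPG it will almost always be filmed. A PUFA-negative tooth is filmed only if it has large caries without visible exposure, symptoms, or signs that PUFA does not record. The Introduction itself notes that chronic apical periodontitis is often free of symptoms. Lesions in unfilmed PUFA-negative teeth can be missed by the reference, and they then count as true negatives instead of false negatives. Blinding the PUFA and PAI readers does not help, because the film trigger and PUFA respond to the same clinical findings.

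At stake is PUFA sensitivity against the apical diagnosis (specific objective c). The error would run towards the hypothesis that PUFA is highly accurate, and more teeth would not shrink it.

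**Working it through.** **1. The plan's own figures.** The half-width is not stated, but 0.10 at 95% confidence reproduces the sample size:
- Sensitivity: 1.96² × 0.50 × 0.50 / 0.10² / 0.05 = 1920.8, so 1921 teeth.
- Specificity: 1.96² × 0.80 × 0.20 / 0.10² / 0.95 = 64.7, so 65 teeth.
- Patients: 1921/12 = 160.1, so 161; 161/0.98 = 164.3, so 165.

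A bias can be judged against that ±0.10.

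**2. Bias from missed lesions, imaging only.** Let f be the share of PUFA-negative, OPG-negative lesions that are filmed (not given in the protocol). Assume that all such PUFA-positive lesions are filmed and that film finds everything OPG finds. Detection is then a = 0.55 in PUFA-positive and b = 0.28 + 0.27f in PUFA-negative lesions. At true sensitivity 0.50 the observed value is a/(a + b).

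| f | b | observed | bias |
|---|---|---|---|
| 0 | 0.280 | 0.663 | 0.163 |
| 0.25 | 0.3475 | 0.613 | 0.113 |
| 0.50 | 0.415 | 0.570 | 0.070 |
| 0.75 | 0.4825 | 0.533 | 0.033 |
| 1 | 0.550 | 0.500 | 0 |

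The bias is 0.05 or less only if f is at least about 0.63.

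**3. Allowing for clinical diagnosis.** Suppose a share c of lesions is diagnosed clinically whatever the image shows, equally in both PUFA groups. Such lesions would normally meet the film trigger, so they are part of f. Then a = c + (1 − c) × 0.55 and b = c + (1 − c) × (0.28 + 0.27 × (f − c)/(1 − c)).
- c = 0.25: bias 0.057 at f = 0.50 and 0.027 at f = 0.75.
- c = 0.50: bias 0.048 at f = 0.50 and 0.023 at f = 0.75.

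These values of c and f are assumptions, so the resulting 0.02 to 0.06 is only an illustration.

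**4. Film false positives.** Film specificity 0.98 mislabels 2% of filmed healthy teeth. Assume all healthy PUFA-positive teeth are filmed, and let g be the filmed share of healthy PUFA-negative teeth. Take imaging only, f = 0.50, prevalence 5%, PUFA sensitivity 0.50 and specificity 0.80. Then, as shares of all teeth:
- TP = 0.025 × 0.55 + 0.95 × 0.20 × 0.02 = 0.01755.
- FN = 0.025 × 0.415 + 0.95 × 0.80 × 0.02 × g = 0.010375 + 0.0152g.
- g = 0.10: 0.01755/(0.01755 + 0.011895) = 0.596, a bias of 0.096.
- The bias is zero when g = (0.01755 − 0.010375)/0.0152 = 0.47.

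With PUFA specificity 0.95 (an assumption) it is zero at g = (0.0147 − 0.010375)/0.01805 = 0.24. The unknown g can therefore raise the bias or remove it.

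**5. Would filming every tooth help?** With the inputs of step 4, f = 1 and g = 1: TP = 0.01755, FN = 0.01375 + 0.0152 = 0.02895, and observed sensitivity is 0.01755/0.0465 = 0.377. That is 0.123 too low, because at 5% prevalence false positives in healthy teeth swamp the missed lesions.

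**6. Would an apical diagnosis made before the film help?** With 165 × 12 = 1980 teeth, 5% gives 99 diseased. On OPG alone 99 × 0.28 = 27.7 would be detected, a half-width of 1.96 × √(0.25/27.7) = 0.186, ignoring clustering. If c = 0.25, 99 × (0.25 + 0.75 × 0.28) = 45.5 are detected, a half-width of 0.145. The protocol also says that "the use of these conventional imaging tends to detect only advanced lesions". If OPG saw 0.33 of PUFA-positive and 0.23 of PUFA-negative lesions (an assumption with mean 0.28), this reference would give 0.33/0.56 = 0.589 when the truth is 0.50, and 0.4975/0.92 = 0.541 at c = 0.25.

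**7. Would a correction formula help?** Multiplying the false-negative term by a/b needs c and f, which concern truly diseased teeth. Counts of filmed teeth cannot supply them, because most teeth are healthy. It also ignores false positives. Take a = 0.6625 and b = 0.56125 (c = 0.25, with half of the lesions not diagnosed clinically filmed) and a true value of 0.500. The formula returns 0.526 with specificity 0.80 and g = 0.10, and 0.457 with specificity 0.95 and g = 0.20.

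**The case for a change.** The strongest case for acting is that the protocol itself fixes the verification rule, that the likely direction favours its hypothesis, and that an apical diagnosis made before the film is lost if nobody records it at the examination. Recording it, with the reason for each film, would need no extra exposure or staff. With the cited sensitivities the error could exceed the ±0.10 that the sample size implies.

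Much of this stands. The mechanism is in the text, and nothing in the documents entitles anyone to call the effect small. The likely direction is upward unless many healthy PUFA-negative teeth are filmed. What does not stand is the gain. The extra reference diagnosis could not resolve a bias of a few hundredths, may carry a spectrum error as large, and has no radiographic basis in teeth whose OPG was unreadable. The films themselves show in part which teeth were filmed. Recording fields and a descriptive table are matters that a protocol commonly leaves to data forms or a statistical analysis plan.

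Two features also lessen the effect without removing it. The reference is a clinical diagnosis that images only support. Patients come from a clinic that "routinely ordered OPG for patients with multiple dental problems", so some PUFA-negative lesions will be filmed or diagnosed clinically.

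**Conclusion.** No change to the plan is needed. PUFA's apical sensitivity may be overstated through differential verification, by 0 to about 0.16 under the protocol's 0.55, 0.28 and 0.50. That range assumes imaging-only detection, film for all OPG-negative PUFA-positive lesions, and no false positives. Allowing for film false positives moves the figure either way, and none of the shares that would settle it is in the documents. NPV moves little: at 5% prevalence and specificity 0.80 it is 1 − 0.025 × 0.28/0.785 = 0.991 with no PUFA-negative lesion filmed and 1 − 0.025 × 0.55/0.785 = 0.982 with all filmed.

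The film rule is a fair trade-off, stated with its reason. It limits exposure and puts the better image where suspicion is highest, and universal filming would not give an unbiased reference under the same figures. The main estimate would stay the same under every remedy considered. A careful analyst will name differential verification as a limitation beside the apical PUFA sensitivity. No conclusion is drawn for the pulpal diagnosis or for the PUFA–PAI contrast.

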Apart from the issue of accuracy, the use of panoramic radiographs were controversial, especially in striking a balance between increased radiation exposures, cost to the health care system and diagnostic yield (Rushton et al. 2001). Panoramic radiographs, in combination with a limited number of intra-oral radiographs, yield good diagnostic information with low radiation dose (Molander et al 1993). Therefore, many dentists reported using it for screening oral diseases in new patients (Rushton et al 1999). Although many radiological findings could be observed on panoramic radiographs, Rushton et al. (2001) argued against its use because the findings are also revealed on bitewing radiographs, or are often not contributive towards treatment planning.

Problem Statement

The PUFA index complements the widely used DMFT index by recording the advancement of the caries lesion into surrounding tissues, which includes pulpal involvement (P), ulceration due to tooth fragments (U), fistula formation (F) and abscess (A). However, this new index has yet to be validated, hence limits its use in prevalence study. On the hand, despite the importance of radiological diagnosis, screening pulpal and periapical diseases using panoramic radiographs (orthopantomographs OPG) are plagued with issues of accuracy and radiation risk. Therefore, comparison of the two screening methods, using PUFA index or panoramic radiograph, will inform clinicians and researchers in selecting the appropriate tool for screening pulpal and periapical diseases.

Research Questions

- a. How reliable is the PUFA in screening pulpal and periapical diseases?
- b. How reliable is the PAI in screening pulpal and periapical diseases?
- c. How accurate is the PUFA in screening pulpal and periapical diseases?
- d. How accurate is the PAI in screening pulpal and periapical diseases?
- e. Is there a difference in the accuracy of PUFA and PAI in screening pulpal and periapical diseases?

Hypotheses

- a. The PUFA index is highly reliable in screening pulpal and periapical diseases.
- b. The PAI is highly reliable in screening pulpal and periapical diseases.
- c. The PUFA index is highly accurate in screening pulpal and periapical diseases.
- d. The PAI is highly accurate in screening pulpal and periapical diseases.
- e. There is a difference in the accuracy of PUFA and PAI in screening pulpal and periapical diseases.

Research Objective

General Objective:

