Ethics approvals will be obtained from the research ethics committee of the university. The research will be conducted in accordance with the Declaration of Helsinki. Informed consent will be obtained from all participants in written form. Emergency treatment will be carried out if the patient is in pain or showing sign of systemic spread of infection (e.g. swelling, fever). Following the study, all participants will be arranged for appropriate treatment.

Data analysis

The demographic data of the patients will be analyzed using descriptive statistics. Mean DMFT and PUFA scores will be calculated. The assessment of the teeth will be tabulated.

The pulpal diagnosis and apical diagnosis for each tooth will be dichotomized as Disease or No Disease. To determine the accuracy of the test, the outcome of PUFA is dichotomized as Positive ($PUFA > 0$) or Negative ($PUFA = 0$) for each tooth. Similarly, the PAI was dichotomized as Positive ($PAI \geq 3$) or Negative ($PAI < 3$). Intra- and inter-examiner reliability will be determined using Cohen's kappa. Sensitivity, specificity, positive predictive value and negative predictive value will be calculated. To compare the two index tests, ROC contrast estimation will be computed.

References

- Fejerskov O, Kidd EAM (2003) Dental caries: the disease and its clinical management. Second Edition, Denmark. Blackwell Monksgaard.
- Oral health division, Ministry of Health Malaysia (2011) National Oral Health Plan for Malaysia 2011–2020.
- Figueiredo MJ, de Amorim RG, Leal SC, Mulder J, Frencken JE (2011) Prevalence and severity of clinical consequence of untreated dentine carious lesion in children from a deprived area in Brazil. *Caries Research* **45**, 435–42.
- Petersen PE. The World Oral Health Report (2003) Continuous improvement of oral health in the 21st century –the approach of the WHO Global Oral Health Programme. *Community Dentistry Oral Epidemiology* **15**, 3–24
- Larmas M (2010) Has dental caries prevalence some connection with caries index values in adults? *Caries Research* **44**, 81–4.

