Appendix 1. Flow chart

Appendix 2. Dummy tables

A total of x patients were invited to participate.

X fulfill the inclusion criteria.

X declined to participate because

Table 1. Demographic distribution of the patients examined

	Count (%)	Mean (SD)
Total number of patient assessed		
Gender		
Male		
Female		
Age		
Age		
DMF		
Decayed		
Missing		
Filled		
DMFT		
DMFT > 0		
PUFA		
Pulpal involvement		
Ulceration		
Fistula		
Abscess		
PUFA		
PUFA > 0		

Table 2. Distribution of teeth assessed using DMFT, PUFA, PAI, Pulpal Diagnosis and Periapical Diagnosis

	Count	Percent
Total number of teeth assessed		
DMFT		
Decayed		
Missing		
Filled		
PUFA		
Pulpal involvement		
Ulceration		
Fistula		
Abscess		
PAI		
1		
2		
3		
4		
5		
Pulpal diagnosis		
Normal pulp		
Reversible pulpitis		
Symptomatic irreversible pulpitis		
Asymptomatic irreversible pulpitis		
Pulp necrosis		
Previously treated tooth		
Previously initiated therapy		
Apical diagnosis		
Normal apical tissue		
Symptomatic apical periodontitis		
Asymptomatic apical periodontitis		
Chronic apical abscess		
Acute apical abscess		
Condensing osteitis		

Table 3. Intra- and inter-examiner reliability (Cohen's kappa) of DMFT, PUFA and PAI

	DMFT	PUFA	PAI
Intra-examiner reliability 1			
Intra-examiner reliability 2			
Inter-examiner reliability			

Table 4. Accuracy of PUFA and PAI

	Gold Standard = Pulpal Diagnosis		Gold Standard = Periapical Diagnosis	
	PUFA	PAI	PUFA	PAI
TP				
FN				
TN				
FP				
Sensitivity				
Specificity				
PPV				
NPV				

Table 5. ROC contrast estimation

Gold Standard	Contrast	Estimate	SE	95% Wald Confidence Limits		Chi-square	P
				Lower	Upper		
Pulpal diagnosis	PUFA-PAI						
Periapical diagnosis	PUFA-PAI

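### The only planned comparison of PUFA and PAI is a ROC contrast on dichotomised scores, which averages the sensitivity and specificity differences and lets opposite differences cancel

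*Protocol*

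**What the plan says.** Objective e is "To compare the accuracy of PUFA and PAI in screening pulpal and periapical diseases", and hypothesis e is an undirected difference in accuracy. The Problem Statement gives the purpose: the comparison "will inform clinicians and researchers in selecting the appropriate tool for screening pulpal and periapical diseases".

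The Data analysis section makes PUFA positive when it exceeds 0. It then adds "Similarly, the PAI was dichotomized as Positive", with the cut at 3 or more. Sensitivity, specificity and predictive values are to be calculated for each test. The only method named for comparing the tests is this: "To compare the two index tests, ROC contrast estimation will be computed". The section does not state whether the dichotomised or the full scores enter it.

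The dummy tables in Appendix 2 match this. "Table 4. Accuracy of PUFA and PAI" lists counts, sensitivity, specificity and predictive values for each test, with no row for a difference, a confidence interval or a test. "Table 5. ROC contrast estimation" has one PUFA-minus-PAI row per gold standard (pulpal, periapical), with estimate, SE, Wald limits, chi-square and P.

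**The concern.** A dichotomised test contributes a single point to the ROC plane, so a contrast of two such areas carries no more than the average of sensitivity and specificity. That average gives the two components equal weight, a choice the protocol does not justify.

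Choosing a screening tool turns on the trade-off between missed disease and false positives. If one test is more sensitive and the other more specific, the contrast can be near zero and hypothesis e would be reported as unsupported, although the tools behave very differently. If the contrast is significant, its P value does not say whether the gain is in disease found or in false alarms avoided.

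**Working it through.** **1. The plan's own sample size.** The Participants section gives 1921 teeth (sensitivity), 65 teeth (specificity), 161 patients and then 165. The half-width is not stated; 0.10 reproduces both tooth counts:
- 1.96² × 0.50 × 0.50 / 0.10² / 0.05 = 1920.8, so 1921
- 1.96² × 0.80 × 0.20 / 0.10² / 0.95 = 64.7, so 65
- 1921/12 = 160.1, so 161; 161/0.98 = 164.3, so 165

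At 5% prevalence, 1921 teeth give about 96 diseased and 1825 non-diseased.

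**2. The contrast.** The area under the line through (0,0), (1 − Sp, Se) and (1,1) is (Se + Sp)/2. On simulated binary data this agreed with the Mann-Whitney area (0.6717 both ways). Hence

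contrast = (ΔSe + ΔSp)/2, with Δ = PUFA minus PAI.

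**3. Illustration, periapical standard only.** For PUFA the protocol says: "As there was no prior data, the sensitivity of PUFA was assumed conservatively at 0.50 and specificity at 0.80". For radiographs it says: "periapical and panoramic radiographs were reported with high specificity (0.98 and 1.00, respectively) but low sensitivity (0.55 and 0.28, respectively) when compared against CBCT". Pairing PUFA 0.50/0.80 with panoramic 0.28/1.00:
- areas (0.50 + 0.80)/2 = 0.65 and (0.28 + 1.00)/2 = 0.64
- ΔSe = +0.22, ΔSp = −0.20, contrast = +0.01
- SE = 0.5 × √[(0.25 + 0.28 × 0.72)/96 + (0.16 + 0)/1825] = 0.0346, with the two tests independent within a tooth and teeth independent
- expected 95% CI −0.058 to 0.078; two-sided power at 0.05 is 6.0%

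In 20,000 simulated trials the rejection rate was 6.8% with independent tests, 6.4% with nested tests and 6.4% with minimum overlap.

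**4. Dependence on PAI.** PUFA is held at 0.50/0.80 and the PAI values are assumed. Each cell gives the contrast and its power.

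| PAI Se | PAI Sp 0.90 | PAI Sp 0.95 | PAI Sp 1.00 |
|---|---|---|---|
| 0.28 | +0.060; 41% | +0.035; 17% | +0.010; 6% |
| 0.40 | 0; 5% | −0.025; 11% | −0.050; 28% |
| 0.50 | −0.050; 28% | −0.075; 54% | −0.100; 79% |

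In every cell specificity differs by 0.10 to 0.20. A paired test of that difference has power of at least 0.9998, even at alpha 0.0125 with an assumed design effect of 2. The contrast dilutes it because the diseased teeth supply most of its variance. In the case of step 3 their part is 0.004704, against 0.000088 from the non-diseased teeth, a share of 98.2%. Over the grid the share is 97.2% to 98.3%.

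**5. The converse ambiguity.** Against PUFA 0.50/0.80, an assumed PAI of 0.72/0.80 (sensitivity alone differs) gives −0.11 with 88% power. An assumed PAI of 0.50/1.00 (specificity alone differs) gives −0.10 with 79% power. The two results look alike in Table 5.

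**6. Power of a separate sensitivity comparison.** Take ΔSe = 0.22, 96 diseased teeth and alpha 0.05/4 = 0.0125 (first Holm step). Let ψ be the discordant proportion. Then power = Φ{(0.22√n − 2.498√ψ)/√(ψ − 0.22²)}.

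| Overlap of the tests in diseased teeth | ψ | n = 96 | Design effect 1.5 (n = 64) |
|---|---|---|---|
| independent | 0.50 | 72% | 50% |
| minimum | 0.78 | 48% | 30% |
| nested | 0.22 | 99% | 92% |

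**The case against.** **The input scores are not stated.** If PAI entered on its 1 to 5 scale, its area would not be (Se + Sp)/2, and the figures above would not apply. This stands as a caveat. The dichotomised reading is still much the better supported: dichotomising is the only handling given for accuracy, and no order is stated among ulceration, fistula and abscess. The protocol needs to say which scores are meant in any case.

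**Table 4 lets the reader see which component differs.** True for the point estimates. Inference on hypothesis e still rests on the average alone.

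**Accuracy is named as one quantity, and an SAP could add more.** A single summary is a legitimate choice in principle. Here, though, the protocol fixes both the method and its results table, and the summary does not serve the stated purpose of choosing a tool.

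**The illustration is a mismatched pair.** PUFA 0.50/0.80 was set without data. The 0.28/1.00 figures are against CBCT, whereas this study's reference diagnosis itself uses the OPG, which may raise PAI sensitivity. The grid also has PAI specificity above PUFA's by construction, and nothing covers the pulpal standard. All of this stands: the magnitudes are illustrative.

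**Twelve teeth per patient is a minimum.** With an assumed 24 (165 × 24 = 3960 teeth), contrast power rises to 84% at PAI 0.50/0.95 and 98% at 0.50/1.00. At 0.28/1.00 it is still 7%, because more teeth cannot recover differences that cancel. Leaving the design effect off the contrast only flatters it.

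**Conclusion.** The concern holds, and the protocol should be changed. Read with dichotomised scores, the sole comparison for objective e is half the sum of two differences that may have opposite signs, so neither a null nor a significant result answers the question posed. That conclusion is algebra and needs no numerical assumption beyond the dichotomised reading.

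How much is lost depends on the unknown accuracy of PAI. Over the assumed periapical values, contrast power runs from 5% to 79% while a specificity difference of 0.10 to 0.20 goes without its own test. These figures assume 1921 independent teeth, 5% prevalence and tests independent within a tooth. The protocol gives no PAI or panoramic figures against the pulpal standard, so no size is claimed there.

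**What to change.** For each gold standard, define the comparison for objective e as two paired differences: sensitivity among diseased teeth and specificity among non-diseased teeth. Use a McNemar-type analysis with variance clustered by patient, and give each difference a 95% CI. State one multiplicity rule for the four tests, for example Holm at 0.05. Keep the ROC contrast as a secondary summary, label it as the difference in (Se + Sp)/2, and state that it uses the dichotomised scores.

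The cost is two extra rows per gold standard in Table 5. No new data, eligibility change or larger sample is needed. The drawbacks are the multiplicity rule and the limited power for sensitivity shown in step 6 of the working; the confidence intervals remain informative either way.
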